8.3.1.1. Sensitivity Analyses

Table 3 provides an overview of the primary and sensitivity analyses of the primary endpoint.

Analysis	Description
Primary analysis	Logistic regression where subjects with missing values are assigned asthma worsening status by Week 24 based on discontinuation of study treatment /withdrawal from study reasons
Sensitivity analysis #1: Missing Status Imputed as Asthma Worsening	Logistic regression where subjects with missing values are considered to have asthma worsening by Week 24
Sensitivity analysis #2: Worse Case Imputation	Logistic regression where placebo subjects with missing values are considered to NOT have asthma worsening by Week 24 and GB001 subjects with missing values are considered to have asthma worsening by Week 24
Sensitivity analysis #3: As Observed Analysis	Logistic regression using only those subjects with an observed status for asthma worsening by Week 24
Sensitivity analysis #4: MI	Logistic regression using MI
Sensitivity analysis #5: Per Protocol Population	Logistic regression in per protocol population using the same approach as primary analysis

 Table 3:
 Summary of Primary and Sensitivity Analyses of the Primary Endpoint

MI = multiple imputation

Sensitivity analyses of the primary endpoint will be conducted to evaluate the robustness of treatment effect under different assumptions and imputation algorithms. Sensitivity analyses will utilize the same logistic regression model as the primary analysis.

In general, for all sensitivity analyses, the number and proportion of subjects meeting each component of the primary endpoint, with observed worsening of asthma, and with an assigned status of asthma worsening will be summarized. The exceptions are Sensitivity Analysis #3 where the number of subjects with an assigned status will not be presented given that the analysis is among subjects with an observed status, and Sensitivity Analysis #4 where the number for each component will not be presented as multiple imputation (MI) will be performed for the overall asthma worsening status (yes/no).

8.3.1.1.1. Sensitivity Analysis #1: Missing Status Imputed as Asthma Worsening

A sensitivity analysis will be conducted with all subjects who prematurely withdraw from the study without experiencing asthma worsening by Week 24 considered as having experienced asthma worsening by Week 24.

8.3.1.1.2. Sensitivity Analysis #2: Worst Case Imputation

A worst case sensitivity analysis will be conducted where all placebo subjects who withdraw from study without experiencing asthma worsening are considered as not having asthma

worsening by Week 24 and all GB001 subjects who withdraw from study without experiencing asthma worsening are considered as having asthma worsening by Week 24.

8.3.1.1.3. Sensitivity Analysis #3: As Observed Analysis

An as observed sensitivity analysis will be conducted where only subjects with an observed status for asthma worsening by Week 24 are included.

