2.5. Sample Size Determination

A total sample size of approximately 480 subjects (approximately 120 per treatment group, randomized in a 1:1:1:1 ratio) is estimated to provide 80% power to detect a reduction in odds of 66% between each GB001 group and placebo at an 0.050 two-sided level of significance for the primary endpoint of the proportion of subjects who experience worsening of asthma by Week 24. This assumes the proportion of subjects who experience worsening of asthma by Week 24 is 25% in the placebo group and 10.2% in each GB001 group and a dropout rate of 8%.

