A subject who prematurely withdraws from the study without experiencing asthma worsening will be assigned asthma worsening status by Week 24 (yes/no) based on their discontinuation of study treatment and withdrawal from study reasons as summarized below in Table 2. If a subject's reason for discontinuation of study treatment or withdrawal from study is indicative of lack of efficacy or is an AE indicative of asthma worsening, a determination will be made prior to study unblinding for the interim analysis regarding whether the subject should be considered to have had asthma worsening for the primary endpoint. Otherwise, subjects who prematurely withdraw from the study will be considered to have not experienced asthma worsening for the primary endpoint.

Table 2:Criteria for determination of asthma worsening status for subjects who
prematurely withdraw from the study without experiencing asthma
worsening

Reason for Discontinuation of Study Treatment and/or Withdrawal from Study	Asthma Worsening Status Assigned (Yes/No)
Lack of Efficacy	Yes
AE where the corresponding AE PT reflects asthma worsening including 'asthma'	Yes
Death where death is due to an SAE where the corresponding SAE PT reflects asthma worsening including 'asthma'	Yes
Lost to follow-up, Non-compliance with study drug, Physician decision, Protocol deviation, Withdrawal by Subject, or Other, where further details indicate asthma, asthma worsening, lack of efficacy or prescription of or switch to a new asthma treatment	Yes
AE where the corresponding AE PT does not reflect asthma worsening	No
Death where death is due to an SAE where the corresponding PT does not reflect asthma worsening	No
Lost to follow-up, Non-compliance with study drug, Physician decision, Protocol deviation, Withdrawal by Subject, or Other, where further details do not indicate asthma, asthma worsening, lack of efficacy or prescription of or switch to a new asthma treatment	No

A bar graph of the proportion of subjects meeting the primary endpoint by treatment group and a bar graph of the proportion of subjects meeting each component of the primary endpoint by treatment group will be provided.

The primary endpoint and components will also be presented in a by-subject data listing.

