8.3.1.1.4. Sensitivity Analysis #4: Multiple Imputation

If the number of subjects overall with a missing observed status for asthma worsening by Week 24 is \geq 5%, then the following MI approach will be conducted as a sensitivity analysis.

The dichotomous outcome of asthma worsening by Week 24 will be imputed for subjects who have withdrawn from study without having experienced asthma worsening using a MI approach assuming that these subjects with a missing dichotomous outcome would have similar outcomes to subjects who had an observed status of asthma worsening by Week 24. The dichotomous outcome will be imputed directly as opposed to imputing the individual components of the primary endpoint and then deriving the composite outcome.

The following steps will be performed:

- Intermittent missing values will first be imputed using the Fully Conditional Specification method, which is appropriate for non-monotonic missing data for binary data.
- The monotone missing values will then be multiply imputed using the monotone logistic regression imputation method (Allison, 2005). A monotone missing pattern is such that in the event that a variable is missing it is implied that all subsequent variables are also missing (i.e. once a subject withdraws from study, no additional data is expected for that subject).
- For each stage, MI will be performed within treatment group with covariate adjustment the same as the primary analysis of the primary endpoint and non-missing outcomes for asthma worsening. Should convergence issues occur due to small cell size for the categorical covariates at either stage, they will be removed from the model.
- The primary analysis of the primary endpoint as described in Section 8.3.1 will be performed for each complete, imputed dataset.
- Fifty imputations will be performed.
- Results of the logistic regression on the multiple imputed data sets will be combined to generate an overall estimate and associated variance using Rubin's rules (Rubin, 1987).

The imputed data logistic regression model-based estimates of the proportion of subjects with asthma worsening, ORs, corresponding 95% CIs, and p-values will be reported. Percentage reductions and corresponding 95% CIs will also be provided.

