8.3.1.3. Additional Analyses of the Primary Endpoint

Logistic regression modeling based on an as observed analysis using the same logistic regression model as Sensitivity Analysis #3 will be used to compare each GB001 group with placebo for the following:

- Each individual component of the primary endpoint separately. An individual component will not be analyzed if < 5 total subjects meet the criterion in the ITT population.
- The AM PEF and FEV₁ components only, as they represent worsening of asthma related to lung function.
- The rescue medication, ACQ-5 score, and severe asthma exacerbation components only, as they represent worsening of asthma related to asthma control.

Lastly, the primary endpoint will be analyzed in a manner similar to the primary analysis, but for the timeframe of by the Follow-up Visit (Week 28) rather than by Week 24.

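### The as-observed rule keeps early withdrawals who had an event and drops those who did not; the component models in SAP 8.3.1.3 rest on it and should be replaced by a censored analysis.

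*SAP*

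**What the plan says.** SAP 8.3.1.1.3 and Table 3 describe Sensitivity Analysis #3 as a logistic regression "where only subjects with an observed status for asthma worsening by Week 24 are included". Neither place defines an observed status. The meaning has to be taken from the neighbouring sections. Sections 8.3.1.1.1 and 8.3.1.1.2 assign a status only to subjects who leave the study before any worsening. In 8.3.1.1.4 the outcome "will be imputed for subjects who have withdrawn from study without having experienced asthma worsening using a MI approach". So a subject who leaves after an event has an observed 'yes', and a subject who leaves event-free has no status.

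Section 8.3.1.3 then specifies "Logistic regression modeling based on an as observed analysis using the same logistic regression model as Sensitivity Analysis #3" for each component of the primary endpoint, for AM PEF and FEV1 together, and for rescue use, ACQ-5 and severe exacerbation together. It gives no other handling of withdrawals and does not say whether status refers to the component or to the composite.

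The main analyses of the composite work differently. In the primary analysis (8.3.1), unless the reason for leaving points to asthma worsening or lack of efficacy, "subjects who prematurely withdraw from the study will be considered to have not experienced asthma worsening for the primary endpoint". The Cox and Kaplan-Meier analysis in 8.3.2.2 censors at the last assessment of any component.

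**The concern.** A subject who worsens at Week 4 and withdraws at Week 6 is counted as an event. A subject who withdraws at Week 6 without worsening leaves the denominator. Selection therefore depends on the outcome, even when withdrawal is purely random. The label suggests a completer-type check, but a completer analysis would drop both subjects.

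For the composite this is one sensitivity analysis of five, beside analyses that keep everyone. The component and grouping models in 8.3.1.3 have no binary counterpart under another withdrawal rule. At stake are the size of the reported component proportions and risk differences and, if the arms lose different numbers, the component odds ratios for a given dose.

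**Working it through.** **Inputs from SAP 2.5.** Week 24 risk 25% on placebo and 10.2% on each GB001 dose; "approximately 120 per treatment group, randomized in a 1:1:1:1 ratio"; 8% dropout, not split by arm; testing "at an 0.050 two-sided level of significance for the primary endpoint".

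**Assumptions, not in the documents.** Constant event and withdrawal hazards over 24 weeks, withdrawal unrelated to event risk, and the arm-specific withdrawal rates shown below.

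**The plan's own figure.** The plan says that its sample size "is estimated to provide 80% power to detect a reduction in odds of 66% between each GB001 group and placebo".
- OR = (0.102/0.898)/(0.25/0.75) = 0.341, a 66% reduction.
- n per arm = (1.960 + 0.842)² × [1/(0.25×0.75) + 1/(0.102×0.898)] / (ln 0.341)² = 110.05.
- 110.05/0.92 = 119.6, so 120 per arm and 480 in total. The figure is reproduced.
- With 120 × 0.92 = 110.4 evaluable per arm, the standard error of the log OR is √(16.25/110.4) = 0.384.

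**The as-observed proportion.** With time scaled to 24 weeks, true risk p and withdrawal d, let λ = −ln(1−p) and μ = −ln(1−d).
- Event seen: E = λ/(λ+μ) × [1 − exp(−(λ+μ))]
- Completed without event: C = exp(−(λ+μ)) = (1−p)(1−d)
- Event-free withdrawal, dropped: 1 − E − C
- As-observed proportion = E/(E+C)

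**Placebo, 8% withdrawal.** λ = 0.2877, μ = 0.0834, E = 0.2403, C = 0.75×0.92 = 0.6900. The rule drops 7.0%, and the proportion is 0.2403/0.9303 = 25.8%.

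**GB001, 8% withdrawal.** λ = 0.1076, E = 0.0979, C = 0.898×0.92 = 0.8262. The rule drops 7.6%, and the proportion is 0.0979/0.9241 = 10.6%.

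The risk difference goes from 14.8 to 15.2 points and the OR from 0.341 to 0.340.

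| Withdrawal, placebo / GB001 | Placebo | GB001 | OR (true 0.341) |
|---|---|---|---|
| 8% / 8% | 25.8% | 10.6% | 0.340 |
| 16% / 16% | 26.8% | 11.1% | 0.340 |
| 4% / 12% | 25.4% | 10.8% | 0.356 |
| 12% / 4% | 26.3% | 10.4% | 0.325 |
| 5% / 20% | 25.5% | 11.3% | 0.372 |

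The 4%/12% case multiplies the OR by 1.045. On the log scale that is 0.044, or 0.044/0.384 = 0.115 of a standard error. The 5%/20% case multiplies it by 1.09.

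**Does the shift differ between components?** With no drug effect and 5% vs 15% withdrawal, the as-observed OR is 1.061 at 25% risk and 1.059 at 5% risk. The factor hardly depends on how common the component is.

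**Component or composite status.** For an assumed component at 8.0% vs 3.3% (true OR 0.393), simulated with 4 million subjects per arm, 8%/8% withdrawal gives 0.392 under component status and 0.394 under composite status. Both give about 0.41 at 4%/12%. Under composite status, someone who withdraws after an event on another component stays in as a 'no' for the component analysed, although follow-up of it was incomplete.

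**The case against.** The strongest reply is that the treatment contrast is hardly affected. The only dropout figure in the documents is 8% overall, and at equal withdrawal the OR is unchanged to within 0.001. An 8-point gap between arms is an assumption and moves the log OR by about a tenth of its standard error. Subjects who only stop study treatment are encouraged to stay in the study (Protocol 7.1) and are not dropped by this rule. All of this stands.

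The composite is also well covered: the primary analysis keeps all ITT subjects, two sensitivity analyses assign every event-free withdrawal, and 8.3.2.2 censors. This too stands, and a censored version of Sensitivity Analysis #3 would only repeat 8.3.2.2.

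On components the reply is partly right. Severe exacerbation has a negative binomial model with follow-up time as offset (8.3.2.3). ACQ-5, FEV1 and AM PEF are modelled as change from baseline (8.3.2.1). Component counts are tabulated by arm in 8.3.1, and by component first met in 8.3.2.2. None of these is a modelled comparison of the binary component under another withdrawal rule, so that gap remains.

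A reader might infer that the rule distorts which component drives the result. The figures do not support this: under random withdrawal the shift is nearly the same factor for every component, so their order does not change.

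**Conclusion.** The rule selects on outcome, by clear implication from 8.3.1.1.1 to 8.3.1.1.4, and 8.3.1.3 carries it into the component and grouping models. Under constant hazards and non-informative withdrawal, proportions are pushed up in every arm with any withdrawal: by 0.8 points on placebo at the planned 8%. The OR is essentially unchanged with equal withdrawal. It moves about 4.5% for a 4%/12% split and 9% for 5%/20%, against whichever arm loses more.

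Two further readings go beyond the documents. One is that the bias always works against the drug. If placebo loses more subjects, it favours the drug. Lack of efficacy is a listed reason for withdrawal (Protocol 7.2), and if higher-risk subjects leave before a recorded event, the proportions could even be understated. The documents give no figure from which to size this. The other is that every component analysis drops event-free withdrawals in the same way. That depends on whether component or composite status governs, which the SAP leaves open.

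The point is minor. It does not threaten the primary conclusion, but the component models can be improved cheaply.

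**What to change.** For the component and grouping analyses in 8.3.1.3:
- Include all ITT subjects, using the component event dates already defined in 8.3.2.2.
- Censor event-free subjects at their last assessment of that component, or of the grouping.
- Report the Kaplan-Meier Week 24 risk by arm with a Cox or discrete-time model for each dose versus placebo.
- Keep the as-observed logistic model as supportive, and state whether its status is judged on the component or the composite.

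Sensitivity Analysis #3 can stay as it is if it is labelled as conditioning on outcome.

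The cost is SAP wording and some programming. Section 8.3.2.2 censors on the last assessment of any component, so component-specific censoring dates have to be derived. No new data are needed. The censored analysis uses partial follow-up and removes this bias when withdrawal is non-informative, but it still rests on that assumption.

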8.3.1.1.4. Sensitivity Analysis #4: Multiple Imputation

If the number of subjects overall with a missing observed status for asthma worsening by Week 24 is \geq 5%, then the following MI approach will be conducted as a sensitivity analysis.

The dichotomous outcome of asthma worsening by Week 24 will be imputed for subjects who have withdrawn from study without having experienced asthma worsening using a MI approach assuming that these subjects with a missing dichotomous outcome would have similar outcomes to subjects who had an observed status of asthma worsening by Week 24. The dichotomous outcome will be imputed directly as opposed to imputing the individual components of the primary endpoint and then deriving the composite outcome.

The following steps will be performed:

- Intermittent missing values will first be imputed using the Fully Conditional Specification method, which is appropriate for non-monotonic missing data for binary data.
- The monotone missing values will then be multiply imputed using the monotone logistic regression imputation method (Allison, 2005). A monotone missing pattern is such that in the event that a variable is missing it is implied that all subsequent variables are also missing (i.e. once a subject withdraws from study, no additional data is expected for that subject).
- For each stage, MI will be performed within treatment group with covariate adjustment the same as the primary analysis of the primary endpoint and non-missing outcomes for asthma worsening. Should convergence issues occur due to small cell size for the categorical covariates at either stage, they will be removed from the model.
- The primary analysis of the primary endpoint as described in Section 8.3.1 will be performed for each complete, imputed dataset.
- Fifty imputations will be performed.
- Results of the logistic regression on the multiple imputed data sets will be combined to generate an overall estimate and associated variance using Rubin's rules (Rubin, 1987).

The imputed data logistic regression model-based estimates of the proportion of subjects with asthma worsening, ORs, corresponding 95% CIs, and p-values will be reported. Percentage reductions and corresponding 95% CIs will also be provided.

8.3.1.1.5. Sensitivity Analysis #5: Per Protocol Population

If \geq 5% of subjects in the ITT population are excluded from the per protocol population, then a sensitivity analysis will be conducted in which the primary analysis of the primary endpoint will be repeated in the per protocol population.

8.3.1.2. Evaluation of Dose Response for the Primary Endpoint

A dose response analysis will be conducted to evaluate the relationship between increasing dose and the effect of GB001, using the primary analysis method of the primary endpoint.

A one-sided, asymptotic, Cochran-Armitage test for trend (Cochran, 1954; Armitage, 1955) will be used to test if the response proportion with asthma worsening decreases linearly with increasing dose level (placebo, 20 mg, 40 mg, 60 mg). The p-value from the test will be reported.

For this test, the null hypothesis, H0 ($\Pi_0 = \Pi_{20} = \Pi_{40} = \Pi_{60}$) is: There is no linear trend in binomial proportions of response across increasing levels of dosage.

The alternative hypothesis, (H1) ($\Pi_0 \ge \Pi_{20} \ge \Pi_{40} \ge \Pi_{60}$) is: There is a decreasing trend in binomial proportions of response across increasing levels of dosage.

To further evaluate the dose response relationship, the ORs and corresponding 95% CIs for the 3 pairwise comparisons among each of the GB001 treatment groups will be provided (60 mg vs 20 mg, 60 mg vs 40 mg, 40 mg vs 20 mg). Percentage reductions and corresponding 95% CIs will also be provided.

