4.3. Justification for Dose

This study will assess the dose-response relationship of 3 doses of GB001 (60 mg, 40 mg, and 20 mg) in adult subjects with moderate to severe asthma.

The GB001 40 mg dose was selected based on the anticipated pharmacokinetics (PK) and exposure levels extrapolated from the results of two Phase 2 studies with GB001 (Study PTR-36-201 and ADC3680-07) and based on prior efficacy and safety results from these studies. In Study PTR-36-201, GB001 20 mg and 5 mg doses were evaluated in an asthma treatment withdrawal design. Both doses of GB001 were effective in decreasing the proportion of subjects with asthma worsening/exacerbations as compared to placebo, with the 20 mg dose producing a larger treatment effect (20 mg: 20.8%; 5 mg: 32.7%; placebo: 52.8%). In addition, only the 20 mg dose demonstrated statistical significance for the endpoints of asthma control (ACQ-5) and time to asthma worsening relative to placebo. No improvements in lung function were observed, while less worsening of lung function was seen in the GB001 groups compared to placebo. A comparable safety profile was observed across all treatment arms (including placebo) in this study. Based on this data, the 40 mg dose has been selected for the current study.

To characterize the dose-response curve, 1 dose level below and 1 dose level above the 40 mg dose are included in the current study. The 20 mg dose has been included as a potentially suboptimal dose based on data generated from a Phase 2 study of GB001 versus placebo (Study ADC3680-07). This study found that GB001 20 mg daily produced some efficacy, as measured by improvements in ACQ scores, but this dose level did not result in improvements in lung function. The 60 mg dose is included to assess whether greater efficacy may be achieved beyond that of the 40 mg dose, since no improvements have been seen in lung function with lower doses to date.

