3. GENERAL ANALYSIS AND REPORTING CONVENTIONS

All analyses will be performed using SAS® System (SAS Institute Inc., Cary, NC) version 9.4 or later.

Categorical variables will be summarized using counts (n) and percentages (%) and will be presented in the format "n (xx.x)". If a count is 0, no percentage will be shown. To ensure completeness, summaries for categorical and discrete variables may include all categories, even if no subjects had a value in a particular category. Additionally, for missing data, a category of "Missing" will be presented as needed.

Continuous (cts) variables, unless otherwise stated, will be summarized using descriptive statistics: number of subjects with non-missing data (n), mean, standard deviation (SD), median, 25th and 75th percentiles, minimum, and maximum. Descriptive statistics on select measures may also include the standard error (SE). Rounding rules for reporting cts descriptive summary statistics are as follows:

- If the original values have 0 or 1 decimal places: mean, median, 25th and 75th percentiles will be reported to one more decimal place than the original values, and SD and SE will be reported to 2 more decimal places than the original values
- If the original values have 2 or more decimal places: mean, median, 25th and 75th percentiles, SD, and SE will all be reported to 3 decimal places

Minimum and maximum will always be reported to the same decimal places as the original values, up to a maximum of 3 decimal places.

Efficacy results will be summarized by various measures including but not limited to odds ratios (ORs), hazard ratios, rate ratios, least squares (LS) means, differences in LS means, SEs, p-values, and two-sided confidence intervals (CIs). The ORs, hazard ratios, rate ratios, and corresponding CIs will be reported to 3 decimal places, percentage reductions and corresponding CIs will be reported to 1 decimal place, and SEs, LS means, differences in LS means and corresponding CIs will be reported per the rules above. P-values will be reported to 4 decimal places, with values less than 0.0001 displayed as < 0.0001 and values greater than 0.9999 displayed as > 0.9999. All statistical hypothesis tests will be two-sided with a significance level of 0.050.

Values with "<" or ">" signs will be analyzed without the signs in tables and figures. In bysubject data listings, values will be reported as collected with the sign.

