8.1.3. Multiple Comparisons/Multiplicity

In general, statistical testing of efficacy endpoints will be made without any adjustments for multiplicity, and all statistical hypothesis tests will be two-sided with a significance level of 0.050.

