8.3.2.3. Annualized Rate of Severe Asthma Exacerbations

A severe asthma exacerbation is defined as deterioration of asthma that leads to the use of systemic corticosteroids for at least 3 days, hospitalization, or an Emergency Department visit. Exacerbations for which the courses of systemic corticosteroids are separated by 7 or more days will be counted as separate severe asthma exacerbations.

The number and proportion of subjects with 0, 1, and ≥ 2 severe exacerbations and the annualized rate of severe asthma exacerbations will be summarized. The unadjusted annualized rate of severe exacerbations will be calculated as the total number of severe exacerbations divided by the total number of subject-years of follow-up and will also be summarized.

The total number of severe exacerbations will be analyzed using a negative binomial regression model, with the logarithmic transformation of follow-up time as the offset parameter. The follow-up time is defined as the subject's time on study up to and including Day 174. The model will include terms for treatment group, ICS dose (medium or high) at randomization, region, age at screening, and the number of exacerbations in the past 12 months. If the distribution of severe exacerbation data is under dispersed, or if the negative binomial regression model fails to converge, a Poisson regression model will be used instead of the negative binomial regression model. Exacerbations for which the courses of systemic corticosteroids are separated by 7 or more days will be counted as separate exacerbations.

Rate ratios for each GB001 group versus placebo, corresponding 95% CIs, and p-values will be provided from the model. In addition, the rate ratios and corresponding 95% CIs for the 3 pairwise comparisons among each of the GB001 treatment groups will be provided (60 mg vs 20 mg, 60 mg vs 40 mg, 40 mg vs 20 mg). Lastly, percentage reductions and corresponding 95% CIs will also be provided.

A sensitivity analysis will be performed to include asthma exacerbations that were treated with an intramuscular (IM) injection of systemic corticosteroids for less than 3 days. In this analysis, a severe asthma exacerbation will be defined as deterioration of asthma that leads to the use of oral or intravenous systemic corticosteroids for at least 3 days, the use of IM systemic corticosteroids for at least 1 day, hospitalization, or an Emergency Department visit.

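### The one-sided dose-trend test in SAP 8.3.1.2 has no stated level and conflicts with the SAP's two-sided 0.050 rule; a lesser point is that its p-value alone cannot show a gradient among the three doses

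*SAP*

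**What the plan says.** SAP 8.3.1.2 evaluates dose response for the primary endpoint in two parts.

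- **A trend test.** It is Cochran-Armitage, asymptotic and one-sided, and it is used to "test if the response proportion with asthma worsening decreases linearly with increasing dose level (placebo, 20 mg, 40 mg, 60 mg". The null is equality of all four proportions. The alternative is described as follows: "There is a decreasing trend in binomial proportions of response across increasing levels of dosage". In symbols it is a chain of greater-than-or-equal signs from placebo down to 60 mg. The p-value is to be reported; no significance level is given.
- **Active-dose comparisons.** As a further evaluation of dose response, "the ORs and corresponding 95% CIs for the 3 pairwise comparisons among each of the GB001 treatment groups will be provided": 60 vs 20, 60 vs 40 and 40 vs 20 mg.

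SAP section 3 sets the general rule: "All statistical hypothesis tests will be two-sided with a significance level of 0.050". SAP 8.1.3 repeats the two-sided 0.050 rule in a sentence that begins: "In general, statistical testing of efficacy endpoints will be made without any adjustments for multiplicity".

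Protocol 4.3 gives the purpose: "This study will assess the dose-response relationship of 3 doses of GB001 (60 mg, 40 mg, and 20 mg"). It adds: "The 60 mg dose is included to assess whether greater efficacy may be achieved beyond that of the 40 mg dose".

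**The concern.** **Level and sidedness.** Section 3 allows no exception to two-sided testing, yet 8.3.1.2 plans a one-sided test and does not say at what level. A reader who compares the p-value with the only level in the SAP applies one-sided 0.05. That is twice the error rate in the tested direction that the general rule permits. The alternative as written also contains the null, because four equal proportions satisfy every greater-than-or-equal sign.

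**Interpretation.** Both questions in Protocol 4.3 compare active doses with each other. The only p-value reported for dose response on the primary endpoint includes placebo, so a drug that works equally well at every dose will usually make it significant. The SAP does not say which of its two outputs would support a statement that more drug gives more effect. What is at stake is how the result is read.

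**Working it through.** **Inputs.** From SAP 2.5: 25% worsening on placebo, 10.2% in each GB001 group, about 120 per group, 8% dropout, two-sided 0.050. Evaluable per arm: 120 × 0.92 = 110.4, so 110; results are given for 110 and 120. Assumptions made here: equally spaced scores (0, 20, 40, 60 mg), since the SAP states none, and every scenario marked *assumed* below.

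**1. The plan's own power figure.** OR = (0.102/0.898)/(0.25/0.75) = 0.341, a 66% reduction in odds; |ln OR| = 1.077. With 110 per arm, SE = √[1/(110×0.25×0.75) + 1/(110×0.102×0.898)] = √(0.0485 + 0.0993) = 0.384. Power = Φ(1.077/0.384 − 1.96) = Φ(0.84) = 80.0%. The stated 80% for each dose against placebo reproduces. The SAP states no power for the trend test.

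**2. False-positive rate of the trend.** With all four proportions equal (25% or 10.2%), exact enumeration gives 5.0% at one-sided 0.05 and 2.5% at one-sided 0.025, for both 110 and 120 per arm. The test holds whatever level is chosen. A two-sided 0.050 test spends 0.025 in each direction, so one-sided 0.05 doubles the error rate in the tested direction.

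**3. Power at the planning rates.** Normal approximation, 110 per arm, centred scores −30, −10, 10, 30, mean proportion 0.139:
- mean of the statistic: 110 × Σ(d·p) = −488.4
- SD under the null: √[110 × 0.139 × 0.861 × 2000] = 162.3
- SD under the alternative: √[110 × Σd²p(1−p)] = 172.2
- one-sided 0.05: Φ[(488.4 − 1.645×162.3)/172.2] = Φ(1.29) = 90.1%
- one-sided 0.025: Φ[(488.4 − 1.960×162.3)/172.2] = Φ(0.99) = 83.9%

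Exact enumeration of the binomial distributions gives 90.4% and 84.5%.

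**4. What the trend can and cannot separate.** Exact results, n = 110 / n = 120 per arm:

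| Proportions: placebo/20/40/60 mg | Trend, one-sided 0.05 | Trend, one-sided 0.025 |
|---|---|---|
| Flat doses, 25/10.2/10.2/10.2% (SAP rates) | 90.4 / 92.5% | 84.5 / 87.3% |
| Linear, 25/20.1/15.1/10.2% (assumed) | 92.5 / 94.3% | 86.9 / 89.6% |
| Plateau at 40 mg, 25/20/10.2/10.2% (assumed) | 96.5 / 97.6% | 93.4 / 95.2% |
| Reversed, 25/10.2/12.5/15% (assumed) | 55.4 / 58.4% | 43.7 / 46.8% |

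The flat and linear rows differ by about 2 points. Changing the level lowers every row but does not separate them.

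**5. What the planned odds ratios can separate.** Percentage of trials in which the 95% CI excludes 1 in favour of the higher dose (unadjusted Wald intervals), n = 110 / n = 120:

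| Scenario | 60 vs 20 mg | 60 vs 40 mg |
|---|---|---|
| Flat 10.2% | 2.2 / 2.3% | 2.2 / 2.3% |
| Linear (assumed) | 52.3 / 56.6% | 18.2 / 20.0% |
| Plateau at 40 mg (assumed) | 51.8 / 56.0% | 2.2 / 2.3% |
| Modest, 16/13.1/10.2% on 20/40/60 mg (assumed) | 23.3 / 25.6% | 9.0 / 9.8% |

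The 60 vs 20 mg ratio separates flat doses from a difference between those two doses, but not a steady gradient from a plateau at 40 mg. Only 60 vs 40 mg bears on whether 60 mg adds anything, and its power is low. With flat doses, at least one of the three unadjusted ratios favours the higher dose in 5.7-6.0% of trials.

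**The case against.** The case for leaving the text alone is substantial.

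- **The test is valid and plainly described.** The four levels and the null are written out, placebo is named, and the error rate holds. A zero dose in a trend test is a common choice. This stands. A reader might infer that 90% significance with flat doses is a type I error, or that the test is mislabelled. Neither follows, because the stated null is equality of all four arms and is false in that case.
- **The gradient is already covered.** The same section plans the three active-dose ratios expressly for dose response, and SAP 8.3.1 gives each arm's proportion with its CI and a bar graph by arm, so a flat or reversed pattern would be visible. This stands, and it refutes any suggestion that the SAP has no analysis of the gradient.
- **Nothing hangs on the p-value.** No passage ties a dose decision to it, and dose response is not a listed primary or secondary endpoint. This stands.
- **The specific text overrides the general.** 8.3.1.2 is specific, and 8.1.3 is softened by its opening words. That may excuse the one-sidedness. It does not supply the missing level, and section 3 has no such softening.
- **The alternative is shorthand.** The words beside the symbols do describe a decrease. This is fair; it is a notational correction only.
- **The scenarios are assumptions.** The flat rates were set to size each dose against placebo and are not a dose-response prediction. The other patterns were chosen for this check. The pairwise figures are unadjusted, whereas the section calls for the primary analysis method, a covariate-adjusted logistic model, so they approximate the planned ratios.

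**Conclusion.** The inconsistency between 8.3.1.2 and section 3 is a real defect in the text. Judged at the only stated level, the trend has a 5.0% false-positive rate in the tested direction instead of 2.5%. That depends on the p-value being compared with 0.050; the SAP does not say what it will be compared with, which is the gap.

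The interpretive point is true but minor. The trend p-value is a sound placebo-anchored result that does not by itself support a claim of growing effect among 20, 40 and 60 mg: 90-93% significance with flat doses against 92-94% under the assumed linear decline, at one-sided 0.05. It would go too far to say that the dose-response analysis fails, that a dose decision is compromised, or that 60 vs 20 mg alone would settle the gradient. That ratio favours 60 mg in 52-57% of trials under both the linear and the plateau pattern.

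These sizes rest on 110 to 120 evaluable subjects per arm, equally spaced scores and unadjusted comparisons.

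**What to change.** In SAP 8.3.1.2:

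1. Report the trend at two-sided 0.050 with its direction stated, or keep it one-sided and set the level at 0.025. If it stays one-sided, name it in section 3 as an exception.
2. Write the alternative with at least one strict inequality, so that it no longer contains the null.
3. Add a sentence saying that the four-level test is a placebo-anchored trend, and that any claim of increasing effect among the active doses is read from the three planned odds ratios and 95% CIs together: 60 vs 40 mg for whether 60 mg adds to 40 mg, and 60 vs 20 mg only for a difference between those two doses. Say that these ratios are not adjusted for multiplicity. By contrast, SAP 8.3.2.1.1 uses Tukey's procedure for the pairwise comparisons of ACQ-5 and pre-bronchodilator FEV₁.

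All three are wording changes; no new analysis or data are needed. Item 1 costs about 5 to 6 points of power at the planning rates (90.4% to 84.5% at 110 per arm, 92.5% to 87.3% at 120). Item 2 costs nothing. Item 3 means that a gradient will be claimed less often, because the active-dose comparisons have little power: 18-20% for 60 vs 40 mg even under the assumed linear decline.
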